An initial meeting of the DSMB will be held prior to any subject enrollment in the study in order for the members to review the charter, to form an understanding of the protocol and definitions being used, to establish a meeting schedule, and to review the study modification and/or termination guidelines. Subsequent interim and final review meetings will be held to review and discuss interim and final study data (adverse events, protocol deviations, enrollment summary and tables for overall primary and secondary endpoints). Frequency of meetings will be every six months, unless the board determines otherwise.

Meeting Format

DSMB meetings will generally be conducted by teleconference and coordinated by the PI. A quorum, defined as 2 out of 4 members will be required to hold a DSMB meeting. Critical decisions of the DSMB should be made by unanimous vote. However, if this is not possible, majority vote will decide.

Open and Closed Sessions

The open session may be attended by the PI and study investigators or their designees. Data presented in the open session may include enrollment data, individual adverse event data, baseline characteristics, overall data accuracy and compliance data or issues, and other administrative data. Minutes of the open session will be recorded by the Chair of the DSMB. Minutes will be finalized upon signature of the chairperson and maintained by the DSMB in accordance with applicable statutory regulation.

The closed session will be restricted to the DSMB members. A facilitator or recorder may be requested by the DSMB. Data which may compromise the integrity of the study (e.g., comparative

data) will be analyzed and discussed only in the closed session. The minutes of the closed session will be recorded by the DSMB Chair. Minutes from the closed session will be recorded separately from the minutes of the open session and stored securely by the DSMB Chair. Closed session minutes, finalized by signature of the chairperson, will be maintained in confidence and retained until discarded in accordance with applicable statutory regulation.

Following each meeting, a report separate from the minutes of the open and closed sessions will be sent to the PI describing the DSMB recommendations and rationale for such (see DSMB Communication of Findings and Recommendations).

Study Review Criteria/Stopping Rules and Guidelines

Guidance for the conduct of safety and efficacy analyses, and guidelines / stopping rules will be established prior to the DSMB's first evaluation of data.

Safety Analyses

The primary safety endpoint is mortality as observed during interim analysis. In addition to the primary safety endpoint, the DSMB will monitor the following adverse events:

1. Acute Lung Injury
2. Nosocomial infection
3. MOF (multiple organ failure)
4. Early seizures
5. In-hospital pulmonary embolism
6. Blood and blood component transfusion and resuscitation requirements
7. Adverse Events
8. Unexpected Adverse Events
9. Expected Adverse Events

Stopping Guidelines / Stopping Rules: Safety

Termination or modification may be recommended for any perceived safety concern based on clinical judgment, including but not limited to a higher than anticipated rate for any component of the primary endpoint resulting in adverse events, or unexpected SAEs.

Efficacy Analyses

The primary outcome variable 30 day mortality will be utilized to assess for efficacy of the trial. Accessing this primary outcome variable at each interim analysis will allow early termination of the trial for either lack of efficacy or excessive efficacy.

Adaptive Protocol Modification

There is no planned sample size re-estimation; however if the DSMB reveals a need, the sample size calculation can be re-evaluated.

Consideration of External Data

The DSMB will also consider data from other studies or external sources during its deliberations, if available, as these results may have a profound impact on the status of the patients and design of the current study.

DSMB Reports

Monitoring for Safety

The primary charge of the DSMB is to monitor the study for patient safety. Formal DSMB safety reviews will occur as specified above (see Study Review Criteria/Stopping Rules and Guidelines).

Monitoring for Efficacy

The DSMB will monitor efficacy outcomes to determine relative risk/benefit, futility, or for early termination due to overwhelming efficacy. Interim analyses efficacy reports sent to the DSMB will occur as specified above (see Study Review Criteria/Stopping Rules and Guidelines).

Monitoring for Study Conduct

The DSMB will review data related to study conduct. Data to be reviewed and listed in the DSMB reports includes: enrollment rates over time, time from last patient enrolled to date of report (indication of delay between treatment or follow-up and reporting), summary of protocol violations, and completeness of treatment and follow-up visit data.

Data Flow for Adverse Events

The DSMB will carefully monitor adverse events periodically throughout the duration of the study. This process will be dynamic to include quarterly reviews of all reported SAEs by the DSMB chairperson. The investigators will be expected to report Serious Adverse Events (SAEs) to the PI within 24 hours of knowledge of the event. The PI will then report it to the DSMB within 7 days.

Preparation of Reports to the DSMB

At the scheduled 6 month DSMB meetings, the study statistician will prepare results for the closed session that show outcomes by treatment effect but with the blinds intact. An independent statistician will prepare and distribute reports to the DSMB electronically approximately 7 days prior to the date of each DSMB meeting.

In order to provide the maximum amount of information to the DSMB, the analyses will employ the most recent data (recognizing limitations thereof) available at the time of the analysis. Requests for additional data by the DSMB members will be made to the DSMB chairperson or his or her designee, who will be responsible for communicating the request with the PI.

The DSMB will review the data and discuss the analyses during the closed portion of the scheduled meeting. If in the closed session the DSMB finds blinded results that are concerning, the meeting will be ended and the DSMB will reconvene in closed session within 1 week to be given the same data unblinded. If the meeting is necessary, an additional interim analysis will be added to the two scheduled interim analyses resulting in the need to recalculate alpha spent. We will be cognizant of the logistical and scientific costs associated with this plan when we are considering any unscheduled analysis.

For the interim analyses at 1/3 and 2/3 enrollment points, the biostatistician will create two reports for the DSMB closed session meeting: one with the treatment arms blinded and one with the blinds broken. The biostatistician will first present to the DSMB data with the blinds intact in closed session. If no point estimates are within the range of the *a priori* stopping rules, the statistician will be asked to proceed at that time with presenting a report with the blinds broken. As the alpha accounting for these two interim looks has already been calculated, it will not need to be recalculated.

DSMB Communication of Findings and Recommendations

Following each meeting and within 14 days of the meeting, the chairperson will send findings and recommendations of the DSMB in writing to the PI.

These findings and recommendations can result from both the open and closed sessions of the DSMB. If these findings include serious and potentially consequential recommendations that require immediate action, the chairperson will also promptly notify the PI by phone and/or by email.

PI's Response to DSMB Findings and Recommendations

The PI and co-investigators will review and respond to the DSMB recommendations. The recommendations of the DSMB will not be legally binding but require professional consideration by the recipients. If the DSMB recommends continuation of the study without modification, no formal response will be required. However, if the recommendations request action, such as a recommendation for termination of the study or modification of the protocol, the DSMB will request that the PI provide a formal written response stating whether the recommendations will be followed and the plan for addressing the issues.

It is recognized that the PI may need to consult with regulatory agencies or other consultants before finalizing the response to the DSMB. Upon receipt, the DSMB will consider the PI response and will attempt to resolve relevant issues, resulting in a final decision. Appropriate caution will be necessary during this process to avoid compromising study integrity or the ability of the PI to manage the study, should the study continue. The PI will agree to disseminate the final decision to the appropriate regulatory agencies, IRB, and investigators within an appropriate time.

In the unlikely event of irreconcilable differences, especially regarding study termination or other substantial study modifications, the DSMB may decide to discontinue monitoring the current study and disband. This decision will be communicated to the PI, FDA, and IRBs.

Public disclosure of the PI's final decision or DSMB recommendations will be at the discretion of the PI or their designee. The DSMB will not make any public announcements either as a group or individually.

DSMB Closeout

This study may be terminated under a variety of circumstances including, but not limited to, termination for overwhelming effectiveness, futility, or safety issues per protocol or DSMB monitoring guidelines. Responsibilities of the DSMB with regard to closeout will be to review the final study report to ensure study integrity. The DSMB may recommend continuing action items to the PI based upon the final review.

Confidentiality

All data provided to the DSMB and all deliberations of the DSMB will be privileged and confidential. The DSMB will agree to use this information to accomplish the responsibilities of the DSMB and will not use it for other purposes without written consent from the study PI and co-investigators. No communication of the deliberations or recommendations of the DSMB, either written or oral, will occur except as required for the DSMB to fulfill its responsibilities. Individual DSMB members must not have direct communication regarding the study outside the DSMB (including, but not limited to the investigators, IRB, regulatory agencies, or PI) except as authorized by the DSMB.

Amendments to the DSMB Charter

This DSMB charter can be amended as needed during the course of the study. Information to be included as amendments will be any modifications or supplements to the reports prepared for the DSMB, as well as amendments to other information addressed in this charter. All amendments will be documented with sequential version numbers and revision dates, and will be recorded in the minutes of the DSMB meetings. Each revision will be reviewed and agreed upon by both the study PI and the DSMB. All versions of the charter will be archived in accordance with this document and maintained by the PI.

Clinical Protocol Appendix 4 – Stopping Rules

STAAMP Trial Stopping Rule and Data Monitoring

In concert with the DSMB, prior to initiation of the trial, the final monitoring plan will be developed to serve as the guide to the DSMB's decision-making process concerning early stopping of the trial monitoring safety and efficacy. In making the decision to recommend termination of the study, the DSMB shall be guided by several types of information: (i) a formal stopping rule based on the primary analysis (comparison of treatment groups on the 30 day mortality), (ii) information on safety outcomes by treatment group, (iii) consistency between results for primary and secondary outcomes, and (iv) consistency of treatment effects across subgroups.

1. O'Brien-Fleming spending (z-values and related alpha) of interim boundaries for each look

We have designed this trial with a two interim look before the final analysis. Our power analysis generated assuming a total of 3 sequential tests based on O'Brien-Fleming spending function to determine alpha spending and test boundaries. We will use test of proportions differences, two sided z-test with continuity correction applied and other adjusting techniques. The level of significance will maintain an overall p value of 0.05 according to O'Brien-Fleming stopping boundaries leaving a p value of 0.038; two sided, for the final analysis with a final z-value of 1.993. An independent data and safety monitoring board (DSMB) will periodically review the efficacy and safety data. DSMB will issue related recommendations based on comprehensive data monitoring and substantiated evidences. Two formal interim analyses of efficacy will be performed when 33% and 67% of the expected number of primary events had accrued (about one month after 1/3 and 2/3 of subject accruals). The purpose of our sequential tests is to detect early sign of superior efficacy and detect further apparent futility in the intervention group. This kind of futility monitoring and testing could cause this trial to be stopped as soon as a negative outcome of 30-days mortality is inevitable and thus it is no longer worthwhile continuing the trial to its completion. Such early termination for futility could reduce the enormous expenditures of resources, human and financial, involved in the conduct of trials that ultimately provides negative answers regarding the value of the study medical intervention.

Our trial's lower and upper stopping boundaries have been computed to ensure that the trial Type I and Type II error probabilities of the group sequential plan are according to the study assumptions and design. The upper boundaries are related to the formal efficacy testing at each assigned sample size (expected number of primary events completion at 33%, 67%, and 100%). The lower boundaries are related to the formal futility (safety) testing at each assigned sample size (expected number of primary events completion at 33%, 67%, and 100%). Upper and lower boundaries will be provided to DSMB as a guideline and could be modified by DSMB prior to the trial upon reasonable justifications. With this sequential testing plan based on O'Brien-Fleming spending function, only an absolutely overwhelming treatment intervention can justify the termination of our clinical trial after a third of the subjects have been enrolled and completed a one month of follow up. If the trial has been ordered to stop early because of interim analysis, adjusted p-values will be computed based on the described analysis of our main clinical outcome. Unadjusted p-value will not be considered for final results interpretations.

Our interim analysis is part of our three sequential testing as we have mentioned above. At each of the two interim looks, 30 days-mortality will be pooled across participated centers comparing between the two study groups. Based on the assumed power analysis at each interim look, the z-value will be calculated and checked against the upper and lower values guide lines for that specific check. We have illustrated z-values for the upper and lower boundaries across interim two analyses and final analysis of a total accumulated alpha of 0.05. (Figure and Table below)

Details when Spending = O'Brien-Fleming, N1 = 497, N2 = 497, P1 = 0.10, P2 = 0.16

Look	Time	Lower Bndry	Upper Bndry	Nominal Alpha	Inc Alpha	Total Alpha	Inc Power	Total Power
1	0.33	-3.71030	3.71030	0.000207	0.000207	0.000207	0.018687	0.018687
2	0.67	-2.51142	2.51142	0.012025	0.011890	0.012097	0.399207	0.417894

3 1.00 -1.99302 1.99302 0.046259 0.037903 0.050000 0.382494 0.800388
 Drift 2.82089

Look: These are the sequence numbers of the interim tests.

Time: These are the time points at which the interim tests are conducted. This is also related to proportion of subject accruals

Lower and Upper Boundary: These are the test boundaries. If the computed value of the test statistic z is between these values, the trial should continue. Otherwise, the trial can be stopped.

[figure not shown]
Nominal Alpha: This is the value of alpha for these boundaries if they were used for a single, standalone test. Hence, this is the significance level that must be found for this look in a standard statistical package that does not adjust for multiple looks.

Inc Alpha: This is the amount of alpha that is *spent* by this interim test. It is close to, but not equal to, the value of alpha that would be achieved if only a single test was conducted. The difference is due to the correction that must be made for multiple tests.

Total Alpha: This is the total amount of alpha that is used up to and including the current test.

Inc Power: These are the amounts that are added to the total power at each interim test. They are often called the exit probabilities because they give the probability that significance is found and the trial is stopped, given the alternative hypothesis.

O'Brien-Fleming boundary values are inversely proportional to the square root of information levels on the standardized Z scale (O'Brien and Fleming 1979). The O'Brien-Fleming boundary is conservative in the early stages and tends to stop the trials early only with a small P -value. But the nominal value at the final stage is close to the overall P -value of the design.

The above plot shows the interim boundaries for each look. This plot shows very dramatically that the results must be extremely significant at early looks, but that they are near the single test boundary (1.96 and -1.96) at the last look.

References

2. Lan, K.K.G. and DeMets, D.L. 1983. 'Discrete sequential boundaries for clinical trials.' *Biometrika*, 70, pages 659-663.
3. O'Brien, P.C. and Fleming, T.R. 1979. 'A multiple testing procedure for clinical trials.' *Biometrics*, 35, pages 549-556
4. Pocock, S.J. 1977. 'Group sequential methods in the design and analysis of clinical trials.' *Biometrika*, 64, pages 191-199

2. Eligibility, recruitment, and accrual reporting

Our periodic reports to DSMB will include as well data on recruitment, data completion, data quality, etc. Data will be summarized in tables as listed below of simplicity and clarity. For simplicity and clarity in reading information, data on eligibility, recruitment, and accrual reporting will be summarized in table 1 and figure 1 and 2.

Table 1 Recruitment and Accrual

	Center1		Center2		Center3		Center4		Center5		Total	
Study treatment	A	B	A	B	A	B	A	B	A	B	A	B
Duration of time in weeks since start going life												
Number of Patients screened												
Number of patient eligible for study												
Eligible but not entered in the study												
Drop off / not able to follow up												
Total patient "randomized"												
Average accrual per month												
Data completion (✓)												
Data Quality (✓)												

Figure 2 Overall Accrual

[figure not shown]
[figure not shown]

Figure 3 Accrual by intervention and centers

3. Information on subjects' demographics and illnesses

In details information on subjects' demographics and illnesses will be summarize in table 2

Table 2 Demographics and Baseline Disease Characteristics

	Center1		Center2		Center3		Center4		Center5		Total	
	A	B	A	B	A	B	A	B	A	B	A	B
Patients numbers												
Age, median and range												
Sex (male) n (%)												
Race, N (%)												
White												
Black												
Other												
Average Lowest pre hospital SBP												
Average Heart rate												
Average Perspiration Rate												
Median ISS												
Mechanism of Injury (blunt) (%)												
CPR (%)												
Pre hospital Blood transfusion (%)												
!!!												

4. Monitoring Safety and efficacy

Further and in relation to interim safety analysis, safety data by study groups labeled as Interventional group (Early using of tranexamic acid) and Control group (Standard of care) will be provided periodically to DSMB. These processed data will provide information on safety outcomes by treatment group, ascertain the consistency between results for primary and secondary outcomes, and inspect the consistency of treatment effects across subgroups. Safety data of the study include serious adverse events regarding frequency, anticipated or unanticipated, individual description for each event and dates. Other data will be provided as well as any additional safety analysis upon DSMB request. Mortality will be reported as an overall in our periodic reports (every 6-9 months depends on accrual rate) to DSMB however we will report mortality individually as treatment A and B at each of the trial two formal interim analyses. Data will be summarized in tables (3-6)

Table 3 Possible Adverse effects

	Center1		Center2		Center3		Center4		Center5		Total	
	A	B	A	B	A	B	A	B	A	B	A	B
Patients numbers												
Transfusion related lung injury n, (%)												
Allergic/anaphylactic reaction												
Circulatory overload												
Infection												
Febrile reaction												
Hemolytic reaction												
!!!												
!!!												
!!!!												

Table 4 Unexpected Adverse Effects

	Center1		Center2		Center3		Center4		Center5		Total	
	A	B	A	B	A	B	A	B	A	B	A	B
Patients numbers												
1. n,(%)												
2.												
3.												
4.												

Table 5 Primary outcomes for patients in the Study

	Center1		Center2		Center3		Center4		Center5		Total	
	A	B	A	B	A	B	A	B	A	B	A	B
Number of Patients												
24 hr Mortality n, (%)												
30 day Mortality n, (%)												

Table 6 Secondary outcomes for patients in the Study

	Center1	Center2	Center3	Center4	Center5	Total
--	---------	---------	---------	---------	---------	-------

	A	B	A	B	A	B	A	B	A	B	A	B
Number of Patients												
Hyperfibrinolysis												
Acute lung injury (%)												
Multiple organ failure (%)												
Nosocomial infection (%)												
Improved shock parameters (%)												
Early resuscitation need (%)												
Transfusion requirements (%)												
Early seizures (%)												
Pulmonary embolism (%)												
Reduce or prevent the early coagulopathy as demonstrated by improving presenting INR (%)												
and Rapid thromboelastography parameters (%)												
Reduce the early inflammatory response, plasmin levels, leukocyte, platelet and complement activation (%)												
ICU days												
Ventilation days												
Hospital LOS												
!!!

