J.1.1. Primary Primary Outcome (30 Day Mortality): All randomized subjects will be included in the analysis to test the differences in 30 day mortality. 30 day mortality will be computed at the end of study and stated as a dichotomous variable. For subjects who have not been reported as deceased by day 30 following admission from any of the sources queried we will use multiple imputation under the assumption that the missing data are not missing at random. The process for determining whether or not a subject is deceased at 30 days is described in detail in section (N.6.). If more than 15% of the subjects are missing the 30 day outcome, we will consider this outcome as descriptive only. We will analyze this endpoint as a fixed point in time using a two-sided Mantel-Haenszel (M-H) test taking site, the stratifying variable (strata), into account. The M-H test is robust to lack of homogeneity of odds ratio although power would be reduced. This approach has more power than the survival analysis described below given the potential for crossing hazard functions. We will also test homogeneity of the odds ratios across sites using the Breslow-Day test. We will compute 95% confidence intervals on mortality by treatment group at 30 days. We will also conduct a sensitivity analysis of 30 day mortality to assess the effect of imputation 'as alive' on the treatment group comparisons and confidence limits for the 30 day outcome. To provide further insight we will compute 30-day survival curves. Survival time will be compared between treatment arms using Cox proportional hazards model with site as a covariate. If the proportional hazards assumption is violated we will include a time treatment interaction in the model and choose the appropriate approach. As an additional analysis, we will use the same Cox proportional hazards approach to adjust for baseline covariates such as demographics, injury severity, presenting vital signs, and prehospital time. Since site is a stratifying variable it will be included as a random effect. We will do pre-screening of covariates other than site at the 0.20 level before fitting the final model if our sample size is not sufficient to include all covariates in the model. We would follow the approach above to test for and take crossing hazards into account if applicable. As an additional exploratory analysis we will compare 30-day survival in the two groups adjusting for the covariates listed above and any additional baseline covariates that are imbalanced between treatment groups ($p < 0.10$) using the same screening approach to decrease the number of covariates included in the model, if necessary.

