We have proposed two interim analyses in this trial. We have based our testing on group sequential design that dividing patient entry into a fixed number of equal-sized groups and provides ethical and practical ways to make decision to stop the trial or continue based on repeated significance tests of the accumulated data after each group is evaluated.

According to the above power calculation and following the group sequential method described by O’Brien and Fleming in developing stopping rules to limit the impact of repeated testing on the probability of a Type I error, we will have equally spaced looks at 33%, 67% and 100% of patient accruals. This is equal to 166, 332, and 497 subjects in each group at these three looks. The following table and graph provide in details information in relation to alpha spending functions to determine the test boundaries according to O’Brien-Fleming method.

Details when Spending = O'Brien-Fleming, N1 = 497, N2 =497, P1 = 0.10, P2 = 0.16

Look	Time	Lower Bndry	Upper Bndry	Nominal Alpha	Inc Alpha	Total Alpha	Inc Power	Total Power
1	0.33	-3.71030	3.71030	0.000207	0.000207	0.000207	0.018687	0.018687
2	0.67	-2.51142	2.51142	0.012025	0.011890	0.012097	0.399207	0.417894
3	1.00	-1.99302	1.99302	0.046259	0.037903	0.050000	0.382494	0.800388
Drift 2.82089								

Look: These are the sequence numbers of the interim tests.

Time: These are the time points at which the interim tests are conducted. This is also related to proportion of subject accruals

Lower and Upper Boundary: These are the test boundaries. If the computed value of the test statistic z is between these values, the trial should continue. Otherwise, the trial can be stopped.

[figure not shown]
Nominal Alpha: This is the value of alpha for these boundaries if they were used for a single, standalone test. Hence, this is the significance level that must be found for this look in a standard statistical package that does not adjust for multiple looks.

Inc Alpha: This is the amount of alpha that is *spent* by this interim test. It is close to, but not equal to, the value of alpha that would be achieved if only a single test was conducted. The difference is due to the correction that must be made for multiple tests.

Total Alpha: This is the total amount of alpha that is used up to and including the current test.

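### Appendix 4 gives 0.038 as the final two-sided p value beside z = 1.993, but that z is p = 0.0463; 0.038 is the incremental alpha at look 3

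*Combined protocol and SAP*

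**What the plan says.** Appendix 4, item 1 sets out two interim looks and a final analysis under an O'Brien-Fleming spending function with an overall two-sided alpha of 0.05. It describes the result as "leaving a p value of 0.038; two sided, for the final analysis with a final z-value of 1.993".

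The boundary table in the same appendix, also printed in P.4, gives for look 3 the upper boundary, Nominal Alpha, Inc Alpha and Total Alpha as "1.99302 0.046259 0.037903 0.050000". Both places define Nominal Alpha: "This is the value of alpha for these boundaries if they were used for a single, standalone test", and hence "this is the significance level that must be found for this look in a standard statistical package". Inc Alpha is defined as the amount of alpha spent at a look.

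Appendix 4 states the interim decision rule on the z scale ("the z-value will be calculated and checked against the upper and lower values guide lines for that specific check") and says of the boundaries that "they are near the single test boundary (1.96 and -1.96) at the last look".

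J.1.1 names the primary analysis as a "two-sided Mantel-Haenszel (M-H) test taking site, the stratifying variable (strata), into account". It states no critical level for that test.

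**The concern.** The sentence in Appendix 4 attaches a p value to a z value that does not correspond to it. A reader who applies the z gets one decision rule for 30-day mortality; a reader who applies the p gets a stricter one. The Mantel-Haenszel result will normally be reported as a p value, and this sentence is the only running text that gives a final p cutoff. If the final p fell between the two figures, the threshold would have to be chosen after the data were seen, which prespecification is meant to prevent.

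**Working it through.** **Inputs.** Overall two-sided alpha 0.05; looks at 1/3, 2/3 and 1; 497 per arm; 0.10 versus 0.16; boundaries 3.71030, 2.51142 and 1.99302; drift 2.82089 (P.4 and Appendix 4 tables). Final p 0.038 and z 1.993 (Appendix 4, item 1).

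**1. The printed table reproduces.** The spending function that matches it is 4 × [1 - Φ(z₁₋α/₄ / √t)].

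| Look | Cumulative alpha, computed | Table | Exit probability under the null, computed | Table Inc Alpha |
|---|---|---|---|---|
| 1 | 0.000207 | 0.000207 | 0.000207 | 0.000207 |
| 2 | 0.012097 | 0.012097 | 0.01189 | 0.011890 |
| 3 | 0.0500 | 0.050000 | 0.0379 | 0.037903 |

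The exit probabilities come from recursive numerical integration with the printed boundaries. Power at drift 2.82089 is 0.8004 (table 0.800388).

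**2. The z and the p in the sentence do not match.**

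- p for the stated z: 2 × [1 - Φ(1.99302)] = 0.046259, the table's Nominal Alpha.
- z for the stated p: Φ⁻¹(1 - 0.038/2) = 2.075.
- Source of 0.038: 0.050000 - 0.012097 = 0.037903, the table's Inc Alpha.

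No reasonable variant gives a final nominal level of 0.038. The one-term spending function gives 0.0439, classical O'Brien-Fleming 0.0451, and the printed function with looks at exactly 0.33 and 0.67 gives 0.0462.

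**3. Effect of applying p ≤ 0.038 at the last look, interim boundaries unchanged.**

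- Alpha: 0.012097 + 0.03023 = 0.0423, against 0.0500.
- Power: 0.4179 + 0.3602 = 0.778, against 0.800.

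**4. Outcomes that fall between the two cutoffs** (pooled z, 497 per arm).

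| Deaths | Continuity correction | z | p | z ≥ 1.993 | p ≤ 0.038 |
|---|---|---|---|---|---|
| 80 vs 58 | no | 2.018 | 0.0436 | yes | no |
| 80 vs 57 | yes | 2.024 | 0.0429 | yes | no |
| 80 vs 58 | yes | 1.926 | 0.0541 | no | no |

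For the first row: pooled risk 138/994 = 0.1388; SE = √(0.1388 × 0.8612 × 2/497) = 0.02193; difference 22/497 = 0.04427; z = 2.018. A site-stratified Mantel-Haenszel test with these deaths spread over four equal sites (20/20/20/20 vs 15/15/14/14) gives z = 2.014, p = 0.044. The second row spread the same way (vs 15/14/14/14, corrected) gives z = 2.020, p = 0.043.

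**5. How often.** In 400,000 simulated trials, with pooled uncorrected z at the interims, a Mantel-Haenszel final test and four equal sites of equal risk (an assumption), the share ending between the cutoffs is 2.2% uncorrected and 2.4% corrected under the design effect, and 0.7% and 0.6% under the null.

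**6. Condition on 0.0463.** It holds for the two planned looks. The DSMB Charter allows an unscheduled unblinded look, "resulting in the need to recalculate alpha spent". Under the same spending function, one added look at information 1/6, 1/2, 5/6 or 0.9 (illustrative timings) gives a final level of 0.0463, 0.0461, 0.0410 or 0.0387.

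**7. Side point: continuity correction.** Appendix 4, item 1 says a continuity correction is applied but not at which looks. The K.1 power rows reproduce as 0.900, 0.850 and 0.800 without it, and become 0.882, 0.827 and 0.772 with it. At 0.10 versus 0.16, sequential power is 0.801 if only the interims are corrected and 0.773 if all three looks are.

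**The case against.** The strongest reply is that the documents mostly resolve this themselves. The correct row is printed twice, Nominal Alpha is defined as the level to be met, the boundary rule is stated on z, and the prose puts the last boundary near 1.96. The sentence can also be read as saying how much alpha is left to spend after the interims, and 0.0379 is the right figure for that. On this view one clause mislabels a column, no one using the table would be misled, and the error is conservative.

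Most of this stands: the weight of the text favours 0.0463, type I error is not inflated, and the power loss arises only if someone actually applies 0.038. The alpha-left reading explains how the slip arose but does not rescue the wording, which calls the figure a two-sided p value for the final analysis and ties it to the z boundary. Nothing says the table takes precedence over the text, and J.1.1 gives no level that would settle the matter.

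It is also fair to say that the continuity correction is a separate question and that the Charter already requires recalculation after an added look. Neither bears on 0.038 versus 0.0463. They matter only for how the corrected sentence should be worded.

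**Conclusion.** The sentence is wrong as written. The p that belongs with z = 1.993 is 0.0463, and 0.038 is the incremental alpha at look 3; this follows from the plan's own table and needs no outside assumption. The boundaries and the planned alpha and power are sound.

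The practical effect is small and conservative: at most about 0.008 of alpha and 2.2 percentage points of power if 0.038 were applied, with roughly 2% of trials in the disputed zone under the design effect. That frequency rests on the assumption of four equal sites with equal risk. The correction is still worth making because the figure is a stated decision level for the primary endpoint.

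**What to change.** - **Appendix 4, item 1:** replace the 0.038 p value with a nominal two-sided p of 0.0463 (|z| ≥ 1.993), and label 0.038 as the incremental alpha at the final look.
- **J.1.1:** state that the primary Mantel-Haenszel test is judged at this level if the two interim looks take place as planned, and otherwise at the level recalculated from the spending function.
- **Continuity correction:** add one line saying whether it covers only the interim z-tests or also the final test. If it governs the final test, restate the power figures (about 77% at 0.10 versus 0.16; the 85% row of K.1 becomes about 82.7%).

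The cost is a few lines of wording. The boundaries, sample size and data collection do not change.
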